### 16.1 Justification of Sample Size and Power Analysis

This is a pilot dose-ranging study. No sample size calculations were conducted.

### 16.2 Analysis Populations

All randomized subjects will be accounted for in a listing for subject disposition. All randomized subjects will be included in the intent-to-treat (ITT) population. All subjects administered any amount of investigational product will be included in the Safety population. The per-protocol (PP) population will include all subjects who meet enrollment criteria and receive all doses of investigational product as required by the protocol and who have no major protocol violations. Major protocol violations are defined as follows:

- 1. Failure to properly obtain consent or subject not consented prior to dosing.
- 2. Subject not meeting the entry criteria and enrolled without a written waiver.
- 3. Subject randomized in the incorrect treatment arm.
- 4. Subject given incorrect dose (overdose/under-dose).
- 5. Data not available from the post-dose central laboratory assessment.
- 6. Failure to complete the study.
- 7. Performing study procedure(s) not described in the approved protocol.

All safety and efficacy analyses will be performed on all populations.

#### 16.3 Interim Analysis

A safety review will be conducted after each cohort to confirm proceeding to the next dose level.

### 16.4 Analysis of Baseline Data

Demographic and baseline characteristics will be summarized using descriptive statistics. Continuous variables will be summarized by mean, median, standard deviation (SD), minimum and maximum. Categorical variables will be summarized by counts and percentages.

## 16.5 Analysis of Primary Outcome Measure

The microbiological response of Nu-3 to eliminate pathogenic bacteria will be determined for each group. Aerobic and anaerobic culture and sensitivity will be assessed at screening, after a single dose treatment (Day 1), after a second dose treatment (Day 2), after twice daily for 7 day treatment, at Day 15. An uncorrected chi-square analysis or a Fisher's Exact test will be used to compare each treatment group to the placebo group. An associated p-value less than 0.05 will be used to define statistical significance. An associated p-value less than 0.016 ( $0.05 \div 5$ ; Bonferroni correction) will be considered highly conclusive.

The clinical response of Nu-3 via visual evaluation of the ulcer will be determined for each group. DUSS Score will be assessed at screening, after a single dose treatment (Day 1), after a second dose treatment (Day 2), after twice daily for 7 day treatment, and at Day 15. An uncorrected chi-square analysis or a Fisher's Exact test will be used to compare each treatment group to the placebo group. An associated p-value less than 0.05 will be used to define statistical significance. An associated p-value less than 0.016 ( $0.05 \div 5$ ; Bonferroni correction) will be considered highly conclusive.

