#### Randomization

Randomization will be conducted in blocks of five to a ratio of 4:1 (active:placebo). Qualified subjects will be enrolled and randomized in: 8:8:8:8:8:10 ratio to either Nu-3 at one of five possible dose levels (0.1%, 1%, 2%, 5% and 10% Nu-3 solution in saline (w/v)), or to placebo, respectively.

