#### 8.3 Cohorts

The dose of Nu-3 administered will be escalated in five planned sequential cohorts, with 10 subjects in each cohort, to be administered Placebo (0.9% saline) or Nu-3 doses of 0.1% solution of BisphosphocinTM Nu-3 in 0.9% saline (w/v) (Cohort 1), 1% solution of BisphosphocinTM Nu-3 in 0.9% saline (w/v) (Cohort 2), 2% solution of BisphosphocinTM Nu-3 in 0.9% saline (w/v) (Cohort 4), 10% solution of BisphosphocinTM Nu-3 in 0.9% saline (w/v) (Cohort 5) at twice daily for 7 consecutive days.

Additional cohorts may be enrolled, if needed, as provided by protocol.

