### 8.5 Number of Subjects

Approximately 50 subjects will be enrolled, of which approximately 40 will be exposed to Nu-3. Numbers may vary due to replacement of subjects, addition of cohorts as permitted by protocol, or stopping of study.

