## 3. STUDY OVERVIEW

This is a phase 1/2a prospective, multi-center, blinded, randomized, dose escalation study. This study will be conducted at four investigational sites. Subjects with diabetic chronic foot ulcer(s) and a Diabetic Ulcer Severity Score (DUSS) of 0 to 3, ulcerated area(s) of not more than two ulcers between 0.5 and 6 cm^2, and no underlying DUSS Probing to Bone='Yes' are eligible to be enrolled into the study.

Doses of Nu-3 will be escalated in three planned sequential cohorts with 10 subjects in each cohort. Randomization will be 4:1 active to placebo in each cohort. The dose levels in each cohort are:

- Cohort 1 – 0.1% solution of Nu-3 in 0.9% saline with vehicle
- Cohort 2 – 1% solution of Nu-3 in 0.9% saline with vehicle
- Cohort 3 – 2% solution of Nu-3 in 0.9% saline with vehicle

Each cohort has placebo defined as 0.9% saline with vehicle. Dosing will be twice daily for 7 consecutive days.

Subjects will have scheduled study visits as follows:

- Screening (Day -7 to -4 hours)
- Single dose visit (Day 1)

- Safety review and multiple dose visit (Day 2)
- Safety review visit (Day 9  $\pm$ 1 day)
- Final Visit (Day 15  $\pm$ 2 days)

At the conclusion of each cohort, a Safety Review Committee will review the safety data and determined if it is safe to proceed to the next cohort. The committee includes, but is not limited to the Sponsor's designated Medical Monitor, the Medical Director of the CRO, and the Medical Director of Lakewood Amedex. Additional members can be added as the sponsor deemed appropriate.

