#### **4. GENERAL ANALYSIS CONSIDERATIONS**

The statistical analyses will be reported using summary tables and data listings. For all efficacy parameters, a comparison will be made of each active treatment group versus placebo using the appropriate statistical test. Unless otherwise indicated, all statistical tests will be two-sided and differences will be considered statistically significant if the associated p-value is less than 0.05. Continuous variables will be summarized with means, standard deviations (SD), medians, minimums, and maximums. Categorical variables will be summarized by counts and by percentage of subjects in corresponding categories. All data will be summarized by dose group (cohort), with all placebo subjects combined into one placebo arm.

Individual subject data obtained from the electronic data capture system, study lab, and any derived data will be presented by cohort for each subject in data listings.

The analyses described in this plan are considered *a priori*, in that they have been defined prior to database lock for individual subjects. Any analyses performed subsequent to database lock will be considered post-hoc and exploratory. Post-hoc analyses will be identified in the CSR.

All analyses and tabulations will be performed using SAS® Version 9.4 or higher on a Windows platform. Tables and listings will be presented in PDF format. Upon completion, all SAS® programs will be validated by an independent programmer. In addition, all program output will undergo a senior level statistical review. The validation process will be used to confirm that statistically valid methods have been implemented and that all data manipulations and calculations are accurate. Checks will be made to ensure accuracy, consistency with this plan, consistency within tables, and consistency between tables and corresponding data listings. Upon completion of validation and quality review procedures, all documentation will be collected and filed by the project statistician or designee.

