## **8.2 Analysis of Efficacy Endpoints**

For each dose group, the proportion of subjects with a normal culture at the end of the MAD portion of the study will be compared to the proportion of subjects with a normal culture at the end of the MAD portion of the study for the combined placebo group using a Fisher's exact test. A subject with a normal culture at this time will be considered a success. Any subject with a missing value at the end of the MAD portion of the study will not be included in the analysis. A p-value less than 0.05 will be considered statistically significant and a p-value less than 0.0167, employing a Bonferroni correction for multiple comparisons, will be considered highly conclusive.

For continuous efficacy endpoints, data will be summarized descriptively at and a comparison using the Wilcoxon Rank Sum test between each of dose groups and the combined placebo group will be performed at each visit. For these endpoints, no imputation for missing values will be performed.

For categorical endpoints, a Fisher's exact test will be performed in a similar manner. Subjects missing a value for a secondary endpoint will be considered a failure (counted in the denominator) for that endpoint.

For all tests, a p-value less than 0.05 will be considered statistically significant and a p-value less than 0.0167, employing a Bonferroni correction for multiple comparisons, will be considered highly conclusive. Analysis for each secondary endpoint will be performed on the ITT population and the PP population.

Ulcer measurements and percentage of area reduction will be summarized descriptively by visit and statistical testing using a Wilcoxon Rank Sum test between each dose group and the combined placebo group. For all tests, a p-value less than 0.05 will be considered statistically significant. Analysis for each additional endpoint will be performed on the ITT population and the PP population.

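### Protocol 16.5 prints the Bonferroni cutoff as 0.016 = 0.05 ÷ 5, but 0.05 ÷ 5 is 0.01; for the protocol's five dose comparisons the cutoff is 60% too high

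*Protocol*

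**What the plan says.** Protocol 16.5 has two paragraphs, one on microbiological response and one on clinical response by DUSS score. Each names the test: "An uncorrected chi-square analysis or a Fisher's Exact test will be used to compare each treatment group to the placebo group". Each declares significance at p below 0.05, then adds a stricter tier: "An associated p-value less than 0.016 ( $0.05 \div 5$ ; Bonferroni correction) will be considered highly conclusive".

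The number of comparisons follows from the design. The synopsis says: "Qualified subjects will be enrolled and randomized in: 8:8:8:8:8:10 ratio to either Nu-3 at one of five possible dose levels". Section 8.3 says doses are "escalated in five planned sequential cohorts, with 10 subjects in each cohort", and the table in section 10.2 lists the same five doses with 8 Nu-3 subjects each. That makes five dose-versus-placebo comparisons per endpoint.

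The SAP describes a smaller design in section 3: "Doses of Nu-3 will be escalated in three planned sequential cohorts with 10 subjects in each cohort". Section 4 pools the controls, "with all placebo subjects combined into one placebo arm". Section 8.2 gives its own cutoff, stated twice: "a p-value less than 0.0167, employing a Bonferroni correction for multiple comparisons, will be considered highly conclusive".

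**The concern.** The number and the formula beside it cannot both be right, and they disagree in both paragraphs of 16.5. Five is the count of dose comparisons in the protocol, so the value is the part that fails. The SAP does not settle the matter, because its 0.0167 belongs to three comparisons. The two documents therefore give almost the same cutoff for five comparisons and for three.

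This label is the only criterion in either document that adjusts for multiple comparisons. Under the protocol as printed, the same result can earn it by the value and miss it by the formula. One secondary objective is to support the dose range for later studies, so how an efficacy result is described has some weight.

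**Working it through.** **Inputs.** Overall level 0.05, two-sided (protocol 16 and 16.5). Five doses with 8 subjects each, and 2 placebo subjects in each of five cohorts, 10 pooled (protocol synopsis, 8.3, 8.4, 10.2). SAP design: three doses with 8 subjects each and 3 × 2 = 6 pooled placebo subjects.

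**Can the printed 0.016 be reproduced?** Bonferroni cutoff = 0.05 ÷ k.

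| k | 0.05 ÷ k |
|---|---|
| 3 | 0.01667 |
| 4 | 0.0125 |
| 5 | 0.0100 |
| 6 | 0.0083 |
| 10 | 0.0050 |

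Šidák, 1 − 0.95^(1/k), gives 0.01695 for k = 3 and 0.01021 for k = 5. None of these is 0.016. The nearest is 0.05 ÷ 3 cut off, not rounded, at three decimals. A carry-over from a three-dose design is therefore plausible, but no text documents it. The SAP's 0.0167 does reproduce, as 0.05 ÷ 3.

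**Size of the discrepancy.** 0.016 ÷ 0.01 = 1.6, so the cutoff is 60% too high. The Bonferroni bound for five comparisons is 5 × 0.016 = 0.08, against 5 × 0.01 = 0.05.

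**Familywise error with a shared placebo group.** Let p be a common response rate, b the number of placebo responders, and A(b) the probability that a dose group's result against b does not fall below the cutoff. Then familywise error = 1 − Σ P(b) × A(b)^k, with P(b) binomial. I enumerated this exactly and took the maximum over p from 0.005 to 0.995. The figures cover one endpoint at one time point.

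| Design | Test | Cutoff | Worst case |
|---|---|---|---|
| 5 doses, 8 v 10 | Uncorrected chi-square | 0.016 | 7.3% |
| 5 doses, 8 v 10 | Uncorrected chi-square | 0.01 | 3.9% |
| 5 doses, 8 v 10 | Fisher's exact | 0.016 | 3.9% |
| 5 doses, 8 v 10 | Fisher's exact | 0.01 | 1.2% |
| 3 doses, 8 v 6 | Fisher's exact | 0.0167 | 1.9% |
| 3 doses, 8 v 6 | Uncorrected chi-square | 0.0167 | 4.8% |

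For the SAP's Wilcoxon endpoints, a normal approximation with five doses gives 6.8% at 0.016 and 4.4% at 0.01. At these sample sizes it is indicative only.

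**Which results change label?** There are 9 × 11 = 99 possible tables for 8 v 10. Fisher's p is below 0.016 in 22 of them and below 0.01 in 16, so six change. Three of the six favour Nu-3:

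- 8/8 v 4/10, p = 0.0128
- 7/8 v 2/10, p = 0.0152
- 6/8 v 1/10, p = 0.0128

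With the uncorrected chi-square, the tables favouring Nu-3 that change are 7/8 v 3/10 (p = 0.0147) and 4/8 v 0/10 (p = 0.0112).

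**The case against.** The strongest reply is that the SAP governs the analysis and does not carry the faulty sum. Protocol section 16 leaves further analysis detail to the SAP, which drops the division by five and gives a single value that is correct for its own three cohorts. The SAP also names Fisher's exact test for culture and other categorical endpoints. The 7.3% figure therefore belongs to a test the SAP does not plan, and one that suits these numbers poorly: expected counts of at least 5 in every cell of an 8 v 10 table would need at least 12 responders in total and at most 6. Under Fisher's test even 0.016 keeps familywise error at 3.9%. Nothing further hangs on the label either: significance is at an uncorrected 0.05, there is no sample size calculation, the primary objective is safety, and escalation rests on dose-limiting toxicity and safety review.

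Most of this stands, and it limits the consequence. It does not remove the error. The protocol still contradicts itself twice, and nothing says the SAP replaces 16.5. The SAP's fixed 0.0167 is right only if three doses are analysed. With five it is as lenient as 0.016, since no Fisher p-value for 8 v 10 lies between the two.

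A second reply is that the number of doses may itself change, in which case 0.01 could also be wrong. Protocol 8.5 says: "Numbers may vary due to replacement of subjects, addition of cohorts as permitted by protocol, or stopping of study". That is a fair point about the order of the repair: the count should be settled first. A misread digit in the printed formula cannot be excluded, but it appears twice, and a divisor of 3 would not fit five doses.

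**Conclusion.** Wrong as written. For the protocol's five comparisons the cutoff should be 0.01, and the printed 0.016 is 60% above it. The SAP's 0.0167 is adequate for the three-dose design it describes and does not correct the five-dose protocol.

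The statistical effect depends on the test. Familywise error passes 5% with the chi-square test that 16.5 permits, but not with Fisher's test. Both results assume 8 subjects per dose, 10 pooled placebo subjects, a common response rate, and a single endpoint at a single time point; neither cutoff covers the several visits and endpoints. The plain p < 0.05 rule is a separate matter and is untouched by this correction: with five doses its worst case is 10.0% with Fisher and 19.2% with chi-square.

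This should be fixed, although it concerns a secondary evidential label in a pilot safety study and does not affect sample size or escalation.

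**What to change.** Before unblinding, reconcile the number of dose cohorts between the protocol (five) and SAP section 3 (three). Then define the label in both documents as p below 0.05 divided by the number of doses compared with placebo, and print the matching value: 0.01 for five, 0.0167 for three. With five doses, 0.016 becomes 0.01 in both paragraphs of protocol 16.5, and the two occurrences of 0.0167 in SAP 8.2 become 0.01. If the reconciled number is not five, change the divisor and the value in 16.5 together.

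The cost is two edits in the protocol and two in the SAP, plus the cohort reconciliation, which is needed in any case. Sample size and data collection do not change. With five doses the label becomes harder to earn.

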#### 1 SYNOPSIS

Name of Sponsor: Lakewood Amedex Inc

Protocol No.: LAI2014-1

Name of Test Product: BisphosphocinTM Nu-3

Clinical Investigation Center(s): Approximately 2 to 4 sites in USA

**Title of Clinical investigation:** A Phase I/IIa, Randomized Double Blind, Placebo-Controlled, Dose Escalating Study to Evaluate the Safety and Tolerability of Topically Applied BisphosphocinTM Nu-3 on Infected Diabetic Ulcers of Subjects With Type I or II Diabetes Mellitus

**Patient Population:** Male and Female subjects 18-85 years of age suffering from diabetes mellitus and a chronic infected diabetic ulcer(s).

Sample Size: Maximum 50 subjects in total across five study cohorts

**Examination Points:** Day 1, 2, 9, 15

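### Protocol 16.5 sets the highly conclusive threshold at 0.016 and derives it as 0.05 ÷ 5, which is 0.01; the SAP's 0.0167 is right for three dose groups but not for the protocol's five (minor)

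*Protocol*

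**What the plan says.** Protocol 16.5 (Analysis of Primary Outcome Measure) covers microbiological response and DUSS in two parallel paragraphs. Each defines significance as p < 0.05 and then adds a stricter tier: "An associated p-value less than 0.016", with 0.05 ÷ 5 given in brackets as the derivation. On the test, each paragraph says: "An uncorrected chi-square analysis or a Fisher's Exact test will be used to compare each treatment group to the placebo group".

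The protocol text that contains 16.5 plans five doses:
- Section 8.3: "The dose of Nu-3 administered will be escalated in five planned sequential cohorts, with 10 subjects in each cohort".
- Synopsis, Randomization: "Qualified subjects will be enrolled and randomized in: 8:8:8:8:8:10 ratio to either Nu-3 at one of five possible dose levels", with the final 10 being placebo.
- The table in section 10.2 gives 8 active subjects at each of 0.1%, 1%, 2%, 5% and 10%.

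The SAP differs. SAP 3 states: "Doses of Nu-3 will be escalated in three planned sequential cohorts with 10 subjects in each cohort", and stops at 2%. SAP 8.2 states that "a p-value less than 0.0167, employing a Bonferroni correction for multiple comparisons, will be considered highly conclusive", and it names Fisher's exact test for the culture endpoint and the other categorical endpoints. SAP 4 pools all placebo subjects into one arm. The SAP does not print the divisor behind 0.0167.

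**The concern.** The threshold and its printed derivation disagree. A reader cannot tell whether the protocol means 0.01 (the formula) or 0.016 (the number), and only 0.01 fits five comparisons. The SAP then carries a third figure that fits a different number of doses, and the available text does not connect the two.

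At stake is a label. It is the plan's only allowance for multiple comparisons, because significance itself is declared at an unadjusted 0.05 in both documents. Choosing a dose range for later studies is a secondary objective. With eight subjects per dose, a single strong-looking result can gain or lose the label depending on the divisor.

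**Working it through.** **1. The plan's own figure.** Inputs: alpha 0.05 and divisor 5 (protocol 16.5). Formula: threshold = alpha ÷ k.
- k = 5: 0.05 ÷ 5 = 0.0100. The protocol's 0.016 is not reproduced.
- k = 3: 0.05 ÷ 3 = 0.01667, which rounds to the SAP's 0.0167 and truncates to 0.016.
- k = 2, 4 and 6 give 0.025, 0.0125 and 0.0083, so none of these gives either figure. That the SAP divided by 3 is an inference, but it matches its three cohorts.

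The text was read from PDF, so a misread digit is possible. If the printed 5 were really a 3, the divisor would not match the five doses in the same protocol text. Either way 0.016 is not a five-comparison Bonferroni threshold.

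**2. Upper bound for five comparisons (k × threshold).** 5 × 0.016 = 0.080; 5 × 0.0167 = 0.0835; 5 × 0.01 = 0.050. For three comparisons, 3 × 0.0167 = 0.0501. These are ceilings, not attained rates.

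**3. Which Fisher results change label, 8 active v 10 pooled placebo (five cohorts × 2).** There are 9 × 11 = 99 possible tables. By two-sided Fisher p:

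| p range | tables |
|---|---|
| p < 0.01 | 16 |
| 0.01 ≤ p < 0.016 | 6 |
| 0.016 ≤ p < 0.0167 | 0 |
| 0.0167 ≤ p < 0.05 | 8 |

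Three of the six favour Nu-3 and three are mirror images favouring placebo. The three are 6/8 v 1/10 (p = 0.0128), 7/8 v 2/10 (p = 0.0152) and 8/8 v 4/10 (p = 0.0128). For 7/8 v 2/10, p = (360 + 10 + 360 + 10) ÷ 48,620 = 0.0152. No table lies between 0.016 and 0.0167, so the gap between those two figures has no effect here; what matters is either of them against 0.01.

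**4. Attained family-wise error of the label with no drug effect.** Let π be a common normal-culture rate (assumed, 0.05 to 0.95 in steps of 0.05), y the number of placebo subjects with a normal culture, and q(y) the chance that one dose group of 8 gives p below the threshold given y. Then the error is Σ Bin(y; 10, π) × [1 − (1 − q(y))⁵]. This is exact and allows for the shared placebo group. Maxima over π:

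| Test | threshold 0.01 | 0.016 or 0.0167 |
|---|---|---|
| Fisher (SAP 8.2) | 0.012 | 0.039 |
| Uncorrected chi-square (protocol option) | 0.039 | 0.073 |

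At 0.016 the chi-square figure exceeds 0.05 for π from 0.35 to 0.65.

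**5. Three cohorts, 8 v 6 pooled placebo (3 × 2), Fisher at 0.0167.** The maximum is 0.019.

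The rates in steps 4 and 5 are for one binary endpoint at one time point. SAP 8.2 also applies 0.0167 to Wilcoxon tests of the score changes. Attained rates for those were not computed, so only the ceilings in step 2 apply to them.

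**The case against.** The best case for the plan is that the SAP is internally consistent: three cohorts, three comparisons, 0.0167. The protocol allows fewer than five cohorts. The synopsis caps enrolment rather than fixing it ("Maximum 50 subjects in total across five study cohorts"), section 8.5 lets numbers vary, and section 8.10.5.1 lets the sponsor stop escalation at any time. Protocol section 16 leaves the detail to the SAP, and the SAP chose Fisher. With 8 v 10, the smallest expected count is at most 8 × 9 ÷ 18 = 4, so Fisher is the natural choice anyway. All of this stands. It limits the consequence but does not make 0.05 ÷ 5 equal 0.016.

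Three stronger readings are tempting, and the documents do not support them.
- A reader might infer that the label's family-wise error is about 8%. That is the Bonferroni ceiling. Under the SAP's Fisher test the attained rate stays below 0.05 even with five doses. The 0.073 needs both five enrolled doses and the chi-square option, which the SAP does not use.
- A reader might infer that the SAP dropped two doses in error. Fewer cohorts are permitted, and two other protocol texts in the same file plan three. Those two give no Bonferroni threshold, so they do not explain 0.016 either, and any explanation may lie on pages not available here.
- A reader might infer that efficacy claims or escalation decisions are compromised. The label governs neither.

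**Conclusion.** The point holds, as a minor one. Protocol 16.5 is arithmetically wrong in both places where it gives the threshold, and 0.016 is not the Bonferroni threshold for the five comparisons that protocol text plans. SAP 8.2 is right for three dose groups and too lenient for five.

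If five doses are compared using Fisher's test, results with 0.01 ≤ p < 0.0167 carry a label that a five-comparison rule would withhold. The label's attained family-wise error is then at most 0.039 rather than at most 0.012. If only three cohorts are run, no SAP result changes. These figures assume 8 subjects per dose, 2 placebo subjects per cohort pooled across cohorts, no missing cultures and a common response rate under no effect. The arithmetic slip is certain; which cohort count applies cannot be settled from the documents. The p < 0.05 rule, dose escalation and safety conclusions are untouched.

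**What to change.** Before database lock, define the threshold in protocol 16.5 (both paragraphs) and SAP 8.2 as 0.05 ÷ k, where k is the number of dose groups actually compared with pooled placebo: 0.01 if five, 0.0167 if three. Delete 0.016. Defining it through k is better than writing ÷ 3 into protocol 16.5, which would leave a five-dose protocol with a three-comparison divisor. The timing matters because SAP 4 treats analyses performed after database lock as post hoc. The cost is a few words in two documents, with no added subjects, visits or assays.
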